9.4.1 General Considerations

The primary analysis will be based on the initial 16-week, double-blind, placebo-controlled phase of the study, and will compare 2 treatment groups comprising all participants

randomized to benralizumab 30 mg Q4W until Week 16 (n = 80) and all participants randomized to placebo until Week 16 (n = 80).

The primary estimand will be based on participants in the full analysis set (Table 12) and will be used for the analysis of primary and key secondary endpoints. The set of incurrent events for this estimand consists of participants who withdraw from the study and participants who require rescue therapy (refer to Section 6.5.3). The primary estimand will regard these participants as non-responders from the time such events occur up to Week 16. The amount of missing data for this study is expected to be low, as participants who prematurely discontinue IP will be asked to come in for all visits and complete all study assessments up to the end of the study. Any participant with missing data at a specific time point will be considered as a non-responder at that time point.

Additional estimands will be specified in the SAP for the primary and key secondary endpoints to carry out sensitivity analyses for assessing the robustness of results. These sensitivity analyses will explore different methods for handling intercurrent events and different assumptions for missing data. Estimands for secondary, exploratory, and tertiary endpoints will also be specified in the SAP, which will include how intercurrent events will be handled for continuous endpoints. Sensitivity analyses may be carried out for specific secondary endpoints, if deemed necessary to strengthen conclusions drawn from the primary and key secondary endpoints. Full details will be provided in the SAP.

Full details of the analyses and methods to be used for the extension period will be provided in the SAP.

Demography and baseline characteristics will be summarized by treatment for the Full Analysis Set (FAS). If there are major differences between the FAS and safety analysis set, the summaries will also be repeated and presented for the safety analysis set.

9.4.2 Efficacy

9.4.2.1 Primary Endpoint

Proportion of Patients with Skin Clearance at Week 16 Using the IGA Data

The primary endpoint is a binary response that classifies a participant's skin clearance at Week 16 using the IGA score. Participants will be classified as responders if IGA 0/1 (ie, clear or almost clear) and they have a decrease in IGA of 2 or more points relative to baseline. Otherwise, participants will be classified as non-responders.

For the primary analysis, a logistic regression model will be fitted to the primary endpoint using a logit link function. The model will include treatment group and baseline covariates for age (adolescents; adults) and blood eosinophils (< 300 cells/ μ L; \geq 300 cells/ μ L). Sensitivity analyses may also explore the effect of including baseline covariates such as severity of

disease (moderate; severe), presence of staphylococcus aureus (absent; present) and asthma comorbidity (yes; no). The model will be used to estimate the proportion of responders for benralizumab and placebo, the difference between these proportions (benralizumab – placebo) and an odds ratio, with corresponding 95% confidence limits. A p-value, corresponding to a 2-sided test, will be presented to compare the benralizumab and placebo treatment groups. Note that if the logistic regression model does not converge to a solution due to low response rates in certain strata, these data will be analyzed using a Cochran–Mantel–Haenszel test.

To support this analysis, the observed proportion of responders will be summarized using descriptive statistics by treatment group and each scheduled visit up to Week 16. Full details will be provided in the SAP.

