9.2 Sample Size Determination

As a minimum, approximately 160 participants will be recruited into the study and will be randomized to one of the following treatment sequences in a ratio of 1:1:2 (respectively):

- Benralizumab 30 mg Q4W until Week 16, followed by an extension period with benralizumab 30 mg Q4W administered until Week 52 (n = 40)
- Benralizumab 30 mg Q4W until Week 16, followed by an extension period with benralizumab 30 mg Q8W administered until Week 52 (n = 40)
- Placebo Q4W until Week 16, followed by an extension period with benralizumab 30 mg Q4W administered until Week 28, and then benralizumab 30 mg Q8W administered until Week 52 (n = 80).

For the initial 16-week treatment period, the aim is to recruit a minimum of 80 participants into the placebo group and a minimum of 80 participants into the benralizumab 30 mg Q4W

group. (Note that participants who receive benralizumab 30 mg Q4W during the first 16 weeks will be grouped together and considered as a single treatment group.)

To identify responding subpopulations, the randomization will be stratified by age (≥ 12 to < 18 years and ≥ 18 years) and baseline blood eosinophils (< 300 cells/µL, ≥ 300 cells/µL). In total, the aim is to recruit a minimum number of participants per strata across the treatment groups as outlined in Table 11.

Table 11Randomization Stratification

	Baseline blood eosinophils		
	< 300 cells/µL	≥ 300 cells/µL	
Adolescents (≥ 12 to < 18 years), n	30	50	
Adults (≥ 18 years), n	30	50	

n, number

The study will continue to recruit participants until the minimum number of participants per strata is achieved, up to a maximum of 200 patients in total. The purpose of this method of recruitment is to ensure that a broad distribution of participants is recruited across the range of ages and blood eosinophil levels to allow potential identification of responding subpopulations and appropriate cut-offs for future studies, if necessary.

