The sample size calculations that follow are based on the primary endpoint, ie, the proportion of patients with an IGA 0/1 and a decrease in IGA of ≥ 2 points relative to baseline. The calculations are associated with differences between benralizumab 30 mg Q4W and placebo at Week 16 during the initial double-blind, placebo-controlled phase of the study (Figure 2). For the primary analysis, the sample size calculation will power the study to detect a difference between benralizumab 30 mg Q4W and placebo in the overall population. Additional calculations have been provided to ensure that the study is adequately powered to detect treatment differences and consistency of effect in potential subgroups, should efficacy be limited to a subset of the population.

Primary analysis: In the overall population, a minimum of 80 participants per treatment group will provide a high level of power (> 95%) to detect a 30% difference between benralizumab 30 mg Q4W and placebo for the primary endpoint. This calculation is based on a 2-sided test and a 5% significance level and assumes a response rate of 40% for benralizumab 30 mg Q4W and 10% for placebo.

Subgroup analyses: As a benchmark, a minimum of 35 participants per treatment will provide at least 80% power to detect a 30% difference between benralizumab 30 mg Q4W and placebo. (As for the primary analysis, these calculations are based on a 2-sided test and a 5%

significance level, and assumes the same response rates for benralizumab 30 mg Q4W and placebo.) Thus, there is a high probability of detecting differences between treatments in the baseline blood eosinophils \geq 300 cells/µL subgroup (with 50 participants per treatment), in the adult subgroup (with 40 participants per treatment), and in the adolescent subgroup (with 40 participants per treatment). Note that in the baseline blood eosinophils < 300 cells/µL subgroup, 30 participants per treatment group will provide an adequate amount of data to explore treatment differences, and will allow different cut-offs between 'low' and 'high' eosinophils at baseline to be assessed.

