9.4.2.2 Key Secondary Endpoints

Proportion of Patients with Skin Clearance at Week 16 Using the EASI Data The first and third key secondary endpoints are binary responses that classify a participant's skin clearance at Week 16 using the EASI:

- EASI-75 response rate: Participants will be classified as responders if they achieve at least a 75% reduction from baseline in their EASI score at Week 16. Otherwise, participants will be classified as non-responders.
- EASI-90 response rate: Participants will be classified as responders if they achieve at least a 90% reduction from baseline in their EASI score at Week 16. Otherwise, participants will be classified as non-responders.

The statistical analysis described for the primary analysis will be carried out for these key secondary endpoints. To support this analysis, the observed proportion of responders will be summarized for each endpoint using descriptive statistics by treatment group and each scheduled visit up to Week 16. Full details will be provided in the SAP.

Proportion of Patients with Itch at Week 16, Using the Peak Pruritus Numerical Rating Scale (NRS) Data

The second key secondary endpoint is a binary response that will classify a participant as a responder if there is an improvement of 4 or more points in peak pruritus weekly score at Week 16 relative to baseline. Otherwise, participants will be classified as a non-responder. (Note that daily peak pruritus scores are averaged to give a weekly score.)

The statistical analysis described for the primary analysis will be carried out for this key secondary endpoint. To support this analysis, the observed proportion of responders will be summarized using descriptive statistics by treatment group and each scheduled visit up to Week 16. Full details will be provided in the SAP.

Note that a hierarchical testing procedure will be used to control the overall Type I error rate at 5% across the primary and key secondary endpoints. Refer to Section 9.4.6 for more details.

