The model will include change from baseline as the dependent variable (derived for each participant and every scheduled visit up to Week 16); baseline as a continuous covariate; treatment, age (adolescents; adults), baseline blood eosinophils ($< 300 \text{ cells/}\mu\text{L}$; $\geq 300 \text{ cells/}\mu\text{L}$) and visit as categorical covariates; treatment-by-visit as an interaction term. An unstructured variance-covariance matrix will be used to model within-subject errors, and the Kenward-Roger approximation will be used to estimate denominator degrees of freedom and to adjust standard errors. (If the model fails to converge, alternative variance-covariance models will be tried in the following order: Toeplitz, first-order regressive, compound symmetry.) For each visit, the model will be used to estimate the mean change from baseline for each treatment group and the difference versus placebo, with corresponding 95% confidence limits. A p-value, corresponding to a 2-sided test, will be presented to compare the benralizumab and placebo treatment groups at each visit. (The p-values will be nominal, as secondary objectives are not controlled for multiplicity and do not appear in the testing hierarchy.)

The distributional assumptions of the MMRM model will be checked by examining plots of residuals. If the residuals suggest that it is unreasonable to assume that data follow a Normal distribution (eg, data are skewed and the constant variance assumption is not met), alternative models will be explored. For example, data may be log transformed prior to fitting the model, or a non-parametric method may be deemed more appropriate.

To support this analysis, observed means and mean changes from baseline will be summarized using descriptive statistics by treatment group and each scheduled visit up to Week 16. Full details will be provided in the SAP.

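### The primary and itch-responder models leave out the participant's own baseline value; adding it is a cheap improvement to a valid analysis, with almost no gain at the design effect

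*Protocol*

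**What the plan says.** Protocol section 9.4.2.1 defines the primary model in full: "The model will include treatment group and baseline covariates for age (adolescents; adults) and blood eosinophils". These are the two randomization stratification factors of section 6.3.1. The same section lists disease severity (moderate; severe), with *S. aureus* and asthma, as covariates that sensitivity analyses have the option of exploring. If the model does not converge because of low response rates in some strata, a Cochran-Mantel-Haenszel test replaces it.

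Section 9.4.2.2 carries the model over to EASI-75 and EASI-90: "The statistical analysis described for the primary analysis will be carried out for these key secondary endpoints". A matching sentence does so for the itch responder endpoint. None of these models has a term for baseline IGA, EASI or itch.

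The repeated-measures model for change in EASI, in section 9.4.2.3, does include "baseline as a continuous covariate", and that section applies it to the continuous itch score as well.

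All three baseline values are available. Entry requires IGA of 3 or more at randomization and a 7-day average itch of 4 or more (section 5.1), and EASI is scheduled at Visits 1 and 2 (Table 3).

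**The concern.** Two of the responder definitions tie response to the starting value. Everyone enters at IGA 3 or 4, so the requirement of a fall of at least 2 points is met by anyone who reaches IGA 0/1. What differs is the distance: 2 points from IGA 3 to IGA 1, and 3 points from IGA 4. For itch, a participant entering with an average of 4 must reach 0 to show a 4-point improvement, whereas one entering at 9 need only reach 5.

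Severity is not stratified, so its balance between arms is left to chance. If these baselines are prognostic, a model with them gives a somewhat sharper comparison and an estimate that allows for whatever imbalance occurs. The protocol already does this for the continuous scores but not for the endpoints in the testing hierarchy. At stake are some precision and a firm place for the severity-adjusted result. The validity of the test is not in question.

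**Working it through.** **Inputs from Protocol section 9.2.** "This calculation is based on a 2-sided test and a 5% significance level", and it "assumes a response rate of 40% for benralizumab 30 mg Q4W and 10% for placebo". Participants "will be randomized to one of the following treatment sequences in a ratio of 1:1:2", which is 80 versus 80 at Week 16 once the two benralizumab sequences are pooled.

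**Inputs not in the protocol.** The prognostic strength of severity and the share of participants at IGA 4 are not given. Assumed: severity odds ratio 1 to 6, and 40% or 50% severe.

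**1. The stated power reproduces.** The protocol says that "a minimum of 80 participants per treatment group will provide a high level of power (> 95%) to detect a 30% difference".
- Power = Φ{[d − 1.96·√(2p̄(1−p̄)/n)] / √[(p₁(1−p₁)+p₂(1−p₂))/n]}, with d = 0.30, p̄ = 0.25, n = 80.
- Pooled SE = √(0.375/80) = 0.0685. Unpooled SE = √(0.33/80) = 0.0642.
- Φ[(0.30 − 0.1342)/0.0642] = Φ(2.58) = 0.995, which agrees.
- The subgroup benchmark, "a minimum of 35 participants per treatment will provide at least 80% power to detect a 30% difference", gives 0.841, which also agrees.
- At 25% versus 10% with 80 per arm, the same formula gives 0.708.

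**2. Effect of adding severity.** Simulated trials, 80 per arm, Wald test of treatment. The protocol model is compared with the same model plus severity, fitted to the same trials, with marginal response rates held fixed. There were 3000 trials per row for 40% severe and 4000 for 50% severe.

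| True rates | Share severe | Severity odds ratio | Protocol model | Plus severity |
|---|---|---|---|---|
| 40% v 10% | 40% | 1 | 99.4% | 99.4% |
| 40% v 10% | 40% | 3 | 99.6% | 99.7% |
| 25% v 10% | 40% | 1 | 71.2% | 71.0% |
| 25% v 10% | 40% | 2 | 71.5% | 71.9% |
| 25% v 10% | 40% | 3 | 70.1% | 72.0% |
| 25% v 10% | 50% | 3 | 70.6% | 73.2% |
| 25% v 10% | 50% | 4 | 70.9% | 73.2% |
| 25% v 10% | 50% | 6 | 71.3% | 75.2% |

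Monte Carlo error is about 0.1 point at the design rates and up to 0.8 point elsewhere. Repeat simulations at 25% versus 10% with odds ratios 3 to 6 gave gains between about 1.4 and 4 points. The gain is not guaranteed. With severity odds ratio 4 and an independent continuous baseline score (odds ratio 2 per SD), severity alone moved power only from 70.5% to 70.9%; severity and the score together gave 74.0%.

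In the 25% versus 10% runs with odds ratios 3 to 6, the two models disagreed on significance in 5–8% of trials.

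**3. Chance imbalance.** With 40% severe, the SD of the arm difference in severe share is √(2 × 0.4 × 0.6/80) = 0.077. The probability of a difference of 10 points or more is 2[1 − Φ(0.10/0.077)] = 20%. Effect of a 10-point imbalance on the unadjusted risk difference:
- Response 13% (moderate) and 5.5% (severe), which averages to 10%: 0.10 × 0.075 = 0.75 points.
- Response 50% and 25%, which averages to 40%: 0.10 × 0.25 = 2.5 points.

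**4. Cost with few responders.** With 10% response in both arms and 4000 trials, separated or non-convergent fits rose from 7/4000 (0.2%) to 166/4000 (4.2%) at severity odds ratio 3, and from 11/4000 (0.3%) to 321/4000 (8.0%) at odds ratio 4. A separate run gave 0.4% rising to about 3%. Type I error was about 0.04 with or without the term.

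**The case against.** The strongest reply is that nothing here is wrong. Adjusting for exactly the stratification factors is a sound primary analysis, and a further covariate is a choice. That stands.

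It also stands that the protocol designates one primary model, so there is no ambiguity about which result counts. The details of sensitivity analyses are deferred to the SAP, which is not at hand and may turn the option on severity into a commitment. The covariates of the main model, however, are fixed in the protocol itself.

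A reader might infer that leaving severity out biases the comparison. It does not: under randomization, chance imbalance is sampling variation that the confidence interval already reflects. A reader might also infer that the extra power is free. The rise in non-convergence shows that it is not, and the concern is greatest for strict endpoints with few responders.

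The argument from definitions does not extend to EASI-75 and EASI-90. These are percentage reductions, so the threshold scales with the participant's own baseline, and nothing in the protocol shows that baseline EASI predicts reaching it. Nor is the contrast with the repeated-measures model a contradiction, since baseline adjustment is conventional for absolute change in a score.

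Finally, adding a prognostic term changes the conditional odds ratio being estimated. The protocol's summary measure is the difference in proportions, so this affects the secondary presentation more than the headline.

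**Conclusion.** The point holds as a modest recommendation. Baseline IGA and baseline itch are collected, bear on response through the endpoint definitions, and are absent from the models that test the primary and itch endpoints.

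At the protocol's own assumption of 40% versus 10%, the change in power is a few tenths of a point at most. At 25% versus 10%, it is about 1.5 to 4 points under severity odds ratios of 3 to 6, and zero if severity is not prognostic. These odds ratios and the severe share are assumptions; the protocol supports the direction of the effect but gives no size.

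It would be tempting to conclude that the study is underpowered or the primary analysis deficient. The reproduced power of 99.5% and the validity of the planned model rule that out, and no change in sample size follows.

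**What to change.** Before the primary database lock, in the protocol or SAP:

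- Add baseline IGA (3; 4) as a factor to the primary logistic model.
- Add baseline weekly peak pruritus as a continuous covariate to the itch-responder model.
- Baseline EASI in the EASI-responder models is optional, for consistency with the repeated-measures analysis.
- Keep the age-and-eosinophil model as a firm sensitivity analysis.
- State the order of fallback: if the model does not converge, drop the severity term and refit, and move to the Cochran-Mantel-Haenszel test only if that fit also fails.

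The cost is wording and one degree of freedom per model. No new data are needed.

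If the sponsor prefers to keep the present primary model, the minimum is to make the severity-adjusted sensitivity analysis a commitment.

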3 OBJECTIVES AND ENDPOINTS

Table 5 lists the objectives of this study and the endpoints for each objective.

Objectives	Estimand description / Endpoints
Primary	
To compare the clinical efficacy of benralizumab 30 mg with placebo in patients with AD despite treatment with topical medications ^a .	 Population: Full analysis set Endpoint: A binary response giving the proportion of patients with an IGA 0/1 and a decrease in IGA of ≥ 2 points at Week 16 relative to baseline Intercurrent events: Participants who withdraw from the study or require rescue therapy ^b will be considered as non-responders from the time these events occur up to Week 16 Summary measure: Difference in proportions between benralizumab and placebo at Week 16
Secondary	
To compare the effect of benralizumab with placebo on supportive measures of clinical efficacy in patients with AD despite treatment with topical medications ^a .	 Key secondary endpoint ^c: proportion of patients with skin clearance (EASI-75) at Week 16 Key secondary endpoint ^c: proportion of patients with an improvement of ≥ 4 or more points in peak pruritus weekly score at Week 16 Key secondary endpoint ^c: proportion of patients with skin clearance (EASI-90) at Week 16 Proportion of patients with skin clearance (EASI-50) at Week 16 Proportion of patients with skin clearance (EASI-100) at Week 16 Change from baseline in EASI score at Week 16 Change from baseline in POEM score at Week 16 Change from baseline in SCORAD at Week 16
To compare benralizumab with placebo on patient- reported health-related quality of life measures in patients with AD despite treatment with topical medications ^a .	Change from baseline in DLQI and CDLQI at Week 16
To estimate the PK and immunogenicity of benralizumab 30 mg in in patients with AD despite treatment with topical medications ^a .	Serum benralizumab concentrationADA

Table 5Objectives and Endpoints

Table 5 Objectives and Endpoints

 Change from baseline in EASI total score at Week 52. Proportion of patients with an IGA 0/1 and a decrease in IGA of ≥ 2 points at Week 52 relative to baseline Proportion of patients with EASI-75 at Week 52 Other supportive efficacy assessments at Week 52 as appropriate. Safety and tolerability will be evaluated in terms of AEs, Vital signs, and Clinical laboratory values. Assessments related to AEs cover: Occurrence/frequency
AEs, Vital signs, and Clinical laboratory values. Assessments related to AEs cover: • Occurrence/frequency

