9.4.2.3 Secondary Endpoints

Proportion of Patients with Skin Clearance at Week 16 Using the EASI Data Two additional binary responses that classify a participant's skin clearance at Week 16 will be derived from the EASI:

- EASI-50 response rate: Participants will be classified as responders if they achieve at least a 50% reduction from baseline in their EASI score at Week 16. Otherwise, participants will be classified as non-responders.
- EASI-100 response rate: Participants will be classified as responders if they achieve at least a 100% reduction from baseline in their EASI score at Week 16. Otherwise, participants will be classified as non-responders.

The statistical analysis described for the primary analysis will be carried out for each of these endpoints. (The p-values will be nominal, as secondary objectives are not controlled for multiplicity and do not appear in the testing hierarchy.) To support this analysis, the observed proportion of responders will be summarized for each endpoint using descriptive statistics by treatment group and each scheduled visit up to Week 16. Full details will be provided in the SAP.

Assessing Changes in Atopic Dermatitis at Week 16 Using the EASI

The EASI is a continuous outcome that will be completed at the visits specified in the SoA (Table 3) during the initial 16-week treatment period. This endpoint will be analyzed by a Mixed Model Repeated Measures (MMRM) model.

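### The switch from logistic regression to CMH depends only on non-convergence, so an arm with no responders can pass as a converged fit with an unusable odds ratio and, if a Wald test is used, a p-value near 1

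*Protocol*

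**What the plan says.** Section 9.4.2.1 of the protocol states that "a logistic regression model will be fitted to the primary endpoint using a logit link function", with treatment, age group and eosinophil group as terms. The model is to supply the two response proportions, their difference and an odds ratio, each with 95% limits. For the test, the text says only that "A p-value, corresponding to a 2-sided test, will be presented to compare the benralizumab and placebo treatment groups"; it does not say whether this is a Wald, score or likelihood-ratio test.

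There is one fallback: "if the logistic regression model does not converge to a solution due to low response rates in certain strata", then "these data will be analyzed using a Cochran–Mantel–Haenszel test". No other trigger is given, and no estimator is named beside the CMH test. The estimand in Section 3 has as its summary measure the "Difference in proportions between benralizumab and placebo at Week 16".

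The recipe carries over. For EASI-75 and EASI-90, Section 9.4.2.2 says "The statistical analysis described for the primary analysis will be carried out for these key secondary endpoints", with a matching sentence for itch. For EASI-50 and EASI-100, Section 9.4.2.3 says "The statistical analysis described for the primary analysis will be carried out for each of these endpoints".

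**The concern.** The sponsor foresaw sparse data and wrote a safeguard, but tied it to the wrong signal. When one treatment group has no responders, the likelihood keeps rising as the treatment coefficient grows, so no finite maximum exists. Many fitting routines stop when the deviance stops changing, and by that criterion they report convergence with a very large coefficient and a far larger standard error. Others fail or flag the problem. The choice of software would then decide which pre-specified test applies.

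If the fit is kept and the p-value is a Wald p, a clear difference is reported as no evidence at all. Changing the test after seeing such a result would be a post-hoc departure, which Section 9.4 requires to be reported in the study report. The phrase about low response rates in certain strata also points to a different and less harmful pattern, as shown below.

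**Working it through.** **Inputs.** From Section 9.2: 80 per arm, 40% versus 10%, two-sided 5%, and 40 per treatment in each age subgroup. Table 11 gives strata of 30/50/30/50, so 15/25/15/25 per arm. The model is that of Section 9.4.2.1. The responder counts are constructed examples.

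**The plan's own figure.** Normal-approximation power = Φ[(0.30 − 1.96·SE₀)/SE₁].
- SE₀ = √(2 × 0.25 × 0.75/80) = 0.0685.
- SE₁ = √((0.40 × 0.60 + 0.10 × 0.90)/80) = 0.0642.
- Power = Φ(2.58) = 99.5%, which agrees with the stated figure of more than 95%.

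The sample size is not in question.

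**Empty placebo arm.** The planned model was fitted with three routines that reported convergence: a packaged binomial GLM, iteratively reweighted least squares (IRLS) with a relative-deviance stop of 1e-8, and BFGS.

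| Active vs placebo | Wald p: GLM / IRLS / BFGS | Likelihood-ratio p | CMH p | Mantel-Haenszel difference (95% CI) |
|---|---|---|---|---|
| 6/80 vs 0/80 | 0.999 / 0.996 / 0.913 | 0.003 | 0.014 | 0.075 (0.017 to 0.133) |
| 8/80 vs 0/80 | 0.999 / 0.996 / 0.964 | 0.0007 | 0.004 | 0.100 (0.034 to 0.166) |
| 12/80 vs 0/80 | 0.999 / 0.995 / 0.980 | 0.00003 | 0.0004 | 0.150 (0.072 to 0.228) |
| 32/80 vs 0/80 | 0.999 / 0.992 / 0.987 | 4e-13 | 4e-10 | 0.400 (0.293 to 0.507) |

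For 6/80 versus 0/80 the GLM gives a log odds ratio of 22.05 with SE 14,639, so z = 22.05/14,639 = 0.0015 and p = 0.999. A Newton solver failed with a singular matrix in the first three cases and flagged non-convergence in the fourth, so it would have reached CMH.

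**CMH by hand for 6/80 versus 0/80** (responders 1/2/1/2 across strata, all active, no continuity correction). With n per arm and m responders in a stratum, the variance is m(2n − m)/[4(2n − 1)].
- Strata with n = 15, m = 1: 29/116 = 0.250 each.
- Strata with n = 25, m = 2: 96/196 = 0.490 each.
- The total is 2 × (0.250 + 0.490) = 1.480. Observed minus expected is 6 − 3 = 3.
- χ² = 9/1.480 = 6.08, p = 0.014.

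**Empty stratum level, both arms with responders.** With 0/6/0/6 versus 0/2/0/2 across strata, the lower eosinophil level has no responders. The treatment Wald p is 0.037 and CMH p is 0.031. The treatment test remains sound, so this pattern does not call for a switch.

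**How often an arm is empty.** P(no responders) = (1 − p)ⁿ. Only the 10% rate is in the protocol; the others are assumptions.

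| True placebo rate | n = 80 | n = 40 |
|---|---|---|
| 10% (planned, primary endpoint) | 0.02% | 1.5% |
| 5% | 1.7% | 13% |
| 3% | 9% | 30% |
| 2% | 20% | 45% |

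**Which endpoints.** By definition the EASI-100 rate cannot exceed the EASI-90 rate, which cannot exceed the EASI-75 rate, which cannot exceed the EASI-50 rate. Low rates are therefore most plausible for EASI-90 and EASI-100. Counting rescue, withdrawal and missing data as non-response lowers all observed rates further.

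**The case against.** The strongest reply has four parts.

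- **The protocol does not say Wald.** This stands. A likelihood-ratio p (0.003 for 6 versus 0) or a score p (0.013) would not fail. Either way, the odds ratio and limits promised by Section 9.4.2.1 remain unusable.
- **Under separation there is no solution to converge to, so a fair reading of the trigger already reaches CMH.** This is arguable, but it leaves a pre-specified rule to interpretation or to a solver's flag, which is what a trigger should avoid.
- **On documented rates the event hardly ever happens.** This stands for the primary endpoint in the overall population. Every larger probability for 80 per arm uses an assumed rate, and Section 9.4.8 leaves the subgroup method to the SAP.
- **The estimator beside CMH belongs in the SAP.** This largely stands. Section 9.4 promises 95% intervals for all point estimates, Section 9.4.2.1 defers full details, and the SAP was not available for this review.

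A reader might also infer that such a failure would stop the testing hierarchy. The documents do not support that as a realistic risk. EASI-90 is fourth and last in Section 9.4.6, so nothing follows it, and EASI-100 is outside the hierarchy with nominal p-values. Stopping earlier would need an empty arm for EASI-75 or itch after success on the primary endpoint, and no stated rate makes that plausible. Nor do the documents show that empty arms are more likely than for the primary endpoint for EASI-50, EASI-75 or itch.

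**Conclusion.** The point holds as a minor defect in a rule that the protocol itself states. Non-convergence alone is an unreliable trigger: with an empty arm, three routines reported convergence with Wald p-values from 0.91 to 0.999, while a fourth failed or flagged the problem. The distorted p-value depends on a Wald test and on the software; the loss of a usable odds ratio does not depend on the statistic.

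The risk to the primary endpoint is negligible at the planned rate. The exposure lies in EASI-90 and EASI-100, and in subgroups if the same model is used there, at assumed true rates of roughly 5% or lower. A failure at EASI-90 would cost that claim only. It would be tempting to say that the CMH branch leaves the estimand without its summary measure, but the protocol leaves only the estimator unnamed, and the SAP may legitimately supply it.

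**What to change.** Extend the trigger in Section 9.4.2.1, and mirror it in the SAP before the primary database lock, along these lines:

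*If the model does not converge, or if a treatment group has no responders (or only responders), or if complete or quasi-complete separation involving treatment is detected, the p-value is taken from the CMH test stratified by age and eosinophil group, and the difference in proportions is the Mantel-Haenszel stratum-weighted difference with its 95% confidence interval.*

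An empty level of a stratification factor should not trigger the switch by itself, because the treatment test is still sound there. Using CMH for every binary endpoint is not needed to repair the rule.

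The cost is one or two sentences and no new data. The downside is that the fallback branch reports no usable odds ratio.
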